5.8.3. Analysis of Vital Signs

Vital signs (including temperature, blood pressure, pulse, and respiration) will be summarized by baseline and change from baseline to each scheduled assessment time with descriptive statistics. The graphs of mean (or median) value of some vital sign parameter vs. visit will also be plotted.

5.9. Analysis of Pharmacokinetics, Pharmacodynamics and Biomarker Data

5.9.1. Analysis of Drug Concentration Data

Cohort 1 PK Sub-study

The concentrations of REGN10933 and REGN10987 in serum over time will be summarized descriptively for each of the treatment groups.

Cohort 2 Pediatric Patients

The concentrations of REGN10933 and REGN10987 in serum over time will be summarized descriptively by body weight tier and treatment group.

Cohort 3 Pregnant Women

The concentrations of REGN10933 and REGN10987 in serum over time will be summarized descriptively for each of the treatment groups.

5.9.2. Analysis of Pharmacokinetics and Pharmacokinetics/Pharmacodynamics

Exposure-response analyses for virologic, other select efficacy and safety endpoints, and/or biomarkers may be performed, as appropriate.

5.10. Analysis of Immunogenicity Data

5.10.1. Analysis of ADA Data

Immunogenicity variables will be summarized using descriptive statistics.

Immunogenicity will be characterized by the ADA responses and titers observed in subjects in the ADA analysis set.

ADA response categories and titer categories are defined as follows:

ADA response categories:

- ADA Negative, defined as ADA negative response in the ADA assay at all time points, regardless of any missing samples.
- Pre-existing immunoreactivity, defined as either an ADA positive response in the ADA assay at baseline with all post first dose ADA results negative, OR a positive response at baseline with all post first dose ADA responses less than 9-fold over baseline titer levels.
- Treatment-emergent response, defined as an ADA positive response in the ADA assay post first dose when baseline results are negative or missing. The treatment-emergent responses will be further characterized as Persistent, Indeterminate or Transient.
 - Persistent Response Treatment-emergent ADA positive response with two or more consecutive ADA positive sampling time points, separated by at least 16week period (based on nominal sampling time), with no ADA negative samples in between, regardless of any missing samples.
 - Indeterminate Response –Treatment-emergent ADA positive response with only the last collected sample positive in the ADA assay, regardless of any missing samples.
 - Transient Response –Treatment-emergent ADA positive response that is not considered persistent or indeterminate, regardless of any missing samples.
- Treatment-boosted response, defined as a positive response in the ADA assay post first dose that is greater than or equal to 9-fold over baseline titer levels, when baseline results are positive

Titer categories (Maximum titer values)

- Low (titer <1,000)
- Moderate $(1,000 \le \text{titer} \le 10,000)$
- High (titer >10,000)

The following analysis will be provided:

• Number (n) and percent (%) of ADA-negative subjects (pre-existing immunoreactivity or negative in the ADA assays at all time points) by treatment arms

- Number (n) and percent (%) of treatment-emergent ADA positive subjects by treatment arms and ADA titer categories
 - Number (n) and percent (%) of persistent treatment-emergent ADA positive subjects
 - Number (n) and percent (%) of indeterminate treatment-emergent ADA positive subjects
 - Number (n) and percent (%) of transient treatment-emergent ADA positive subjects
- Number (n) and percent (%) of treatment-boosted ADA positive subjects by treatment arms and ADA titer categories

Listing of all ADA titer levels will be provided for subjects with pre-existing, treatment-emergent and treatment-boosted ADA response.

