 - Targeted concomitant medications and concomitant procedures will also be reviewed and recorded. Refer to Section 9.2.4.3 for more information.
- 8. Continuously-monitored events will be recorded when they occur during the corresponding time period marked on the schedule of events. Study visits (including phone calls) are not required solely to collect continuously-monitored assessments, if no other assessments are planned on that day.
- 9. Pregnancy testing will be performed in women of childbearing potential (WOCBP) only and regardless of pregnancy status. A negative test is **not required** prior to study drug

administration. Serum or urine pregnancy test are both acceptable. Refer to Section 9.2.6 for more information, including a definition of WOCBP.

Note that a paper pregnancy report form must be completed for each patient who becomes pregnant or is pregnant at the signing of consent.

- 10. The indicated blood samples may be collected at the either day -1 or day 1 (ie, screening or pre-dose), but must be collected prior to randomization. For patients in phase 3 cohort 2, efforts should be made to collect all screening/pre-dose blood samples on the same study visit, when feasible.
- 11. [Footnote removed]
- 12. Actual dosing time and drug concentration sample collection times, as applicable, will be recorded.

At the screening/baseline visit, blood for assessment of drug concentration in serum will be taken prior to dosing and within 60 minutes after the end of infusion (EOI). The EOI sample should be collected from the arm contralateral to that used for IV infusion. If not medically feasible, the EOI sample can be drawn from the same arm, but not from the infusion catheter.

In cohort 1 and cohort 3 (\geq 18 years old), patients will follow different blood sample collection schedules for drug concentration and immunogenicity depending on whether they enrolled in the PK sub-study (cohort 1), not enrolled in the PK sub-study (cohort 1), or are pregnant at randomization (cohort 3 patients \geq 18 years old). For samples collected on day 120, the collection window is \pm 28 days. Refer to Section 9.2.8 for more information on the PK sub-study.

- 13. The window for predose ADA sample collection is as close to administration of study drug as is reasonable. Actual dosing time and ADA sample collection times, as applicable, will be recorded.

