- 14. On visit days when other assessments or sample collections are required, the site will verify that questionnaires have been completed prior to all other assessments or collections. The order of questionnaire completion is provided below. On days when a questionnaire is not required it will be skipped, but the overall order will remain the same. Refer to Section 9.2 for additional information regarding these questionnaires.

Cohort 1: SE-LC19, PGIS, PGIC, return to usual health, return to usual activities, SF-36, WPAI+CIQ, EQ-5D-5L.

Cohort 2 (≥12 years): SE-C19, PGIS, PGIC, return to usual health, return to usual activities, EQ-5D-Y, WPAI+CIQ.

Cohort 3 (≥12 years): SE-C19, PGIS, PGIC, return to usual health, return to usual activities, EQ-5D-5L (or EQ-5D-Y), WPAI+CIQ.

On days 60 and 90, the window for questionnaire assessment is ± 3 days. On days 120 and 169, the window for questionnaire assessment is ± 7 days. Study visits are not required on days when only questionnaires are collected.

Note that questionnaires will only be administered to sites when regionally available, and will only be administered to patients who are able to complete the questionnaires in the language available at their site.

- 15. In **cohort 2 (and patients <18 years in cohort 3)**, each patient will be assigned at randomization by IWRS to a blood sample collection schedule for drug concentration and immunogenicity analysis. Actual dosing time and PK-ADA sample collection times will be recorded. To conserve blood volume, a single blood draw for drug concentration and immunogenicity will be obtained. In patients <12 years, immunogenicity will be analyzed only in pre-dose and day 29 PK-ADA samples.
- 16. Patients will be followed at day 120 and day 169 for vital status, pregnancy status, targeted safety information, and additional safety information in newborns of study participants. Refer to Section 9.2.5 for more information on these follow-up assessments.
- 17. For patients <12 years in cohort 2 and cohort 3, follow-up by phone will be conducted within 6 to 8 hours of infusion to collect the information indicated.
- 18. Patients in phase 3 cohort 1 will follow the Schedule of Events in Table 5 until day 90. They will then follow the long COVID Schedule of Events Table 6 until day 169.

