9.2.8. Drug Concentration Measurements and Samples

Note: As of protocol amendment 9 US, the PK sub-study is no longer enrolling new participants.

Samples for assessment of drug concentration will be collected at the timepoints indicated in the schedule of events. For information concerning unused samples and exploratory research, refer to Section 9.2.10.

In phase 3 cohort 1, approximately 600 patients will be enrolled in a PK sub-study (refer to Table 5). This sub-study will only be enrolled at a select number of participating sites. In cohort 1, only patients who are enrolled in the PK sub-study will have samples collected for drug concentrations. Additional samples for immunogenicity assessment will be also collected in these patients.

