11.4.8. Analysis of Immunogenicity Data

Immunogenicity will be characterized by the ADA and NAb responses and titers observed in patients in the ADA and NAb analysis sets. ADA response categories and titer categories are defined as follows:

ADA Response Categories:

- ADA Negative, defined as ADA negative response in the ADA assays for all time points regardless of any missing samples
- Pre-existing immunoreactivity, defined as either an ADA positive response in the ADA assay response at baseline with all post first dose ADA results negative, or a positive assay response at baseline with all post first dose ADA assay responses less than 9-fold over baseline titer levels.
- Treatment-emergent response, defined as an ADA positive response in the ADA assay post first dose when baseline results are negative or missing.
- Treatment boosted ADA response, defined as a positive response in the ADA assay post first dose that is greater than or equal to 9-fold over baseline titer levels when baseline results are positive

Titer categories (Maximum titer values):

- Low (titer < 1,000)
- Moderate $(1,000 \le \text{titer} \le 10,000)$
- High (titer > 10,000)

The following analysis will be provided:

- Number (n) and percent (%) of ADA-negative patients (pre-existing immunoreactivity or negative in the ADA assay at all time points) by treatment groups
- Number (n) and percent (%) of treatment-emergent ADA positive patients by treatment groups and ADA titer categories and at the
- Number (n) and percent (%) of treatment-boosted ADA positive patients by treatment groups and ADA titer categories

Listing of all ADA titer levels will be provided for patients with pre-existing, treatment-emergent and treatment-boosted ADA response.

The absolute occurrence (n) and percent of patients (%) with NAb status in the NAb analysis set will be provided by treatment groups.

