3.4. Immunogenicity Analysis Sets

The immunogenicity analysis set is dependent on assay availability.

The anti-drug antibody (ADA) analysis set (AAS) includes all subjects who received any study drug (safety population) and had at least one non-missing ADA result from the ADA assay after first dose of the study drug(s). Subjects will be analyzed according to the treatment actually received.

Samples positive in the ADA assay will be characterized further for ADA titers and for the presence of neutralizing antibody (Nab). The NAb analysis set (NAS) includes all patients who received any study drug and who are either negative in the ADA assay or positive for ADA with at least one non-missing result in the NAb assay after first dose of the study drug. Subjects who are negative for ADA are set to negative in the NAb analysis set

Subjects will be analyzed according to the treatment actually received.

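### One ADA (and NAb) percentage per arm mixes cohort 1 patients sampled only at day 29 with the PK sub-study also sampled at day 120, which dilutes any response first seen late

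*SAP*

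**What the plan says.** SAP 3.4 admits to the ADA analysis set any dosed patient with one usable ADA result after dosing, and sets no minimum length of sampling. SAP 5.10.1 then classifies each patient over whatever samples exist. One class is "Treatment-emergent response, defined as an ADA positive response in the ADA assay post first dose when baseline results are negative or missing". The opposite class is "ADA Negative, defined as ADA negative response in the ADA assay at all time points, regardless of any missing samples". The planned output is "Number (n) and percent (%) of treatment-emergent ADA positive subjects by treatment arms and ADA titer categories", with persistent, indeterminate and transient sub-counts but no split by visit or sampling schedule. SAP 5.10.2 reports NAb status by treatment group. Because SAP 3.4 sets ADA-negative patients to NAb-negative, the NAb percentage takes over the same mixed denominator.

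Sampling is not uniform. Footnote 12 in Protocol 9.1.1 says that in cohort 1 and adult cohort 3 "patients will follow different blood sample collection schedules for drug concentration and immunogenicity depending on whether they enrolled in the PK sub-study". In cohort 1 the schedules give pre-dose and day 29 outside the sub-study, with a day 120 draw added inside it (Protocol 6.1.3.2 and Table 6; SAP 10.1). Protocol 9.2.8 puts the sub-study at about 600 patients and adds: "Additional samples for immunogenicity assessment will be also collected in these patients". Phase 3 patients enrolled before Amendment 6 followed Protocol Table 4, where the last ADA draw is day 29.

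For cohort 2 and cohort 3 patients under 18, Protocol Table 8 (Amendment 10 US) has a day 90 draw on schedules A and B or a day 120 draw on C and D. The SAP schedule, written to Amendment 8, has none after day 29. Footnote 15 adds: "In patients <12 years, immunogenicity will be analyzed only in pre-dose and day 29 PK-ADA samples".

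**The concern.** A patient negative at day 29 and never sampled again counts exactly like one who is still negative at day 120. A response first found at day 120 can be seen only in the sub-study, yet it is divided by everyone in the arm. The share of late-tested patients also differs by arm, because placebo, 2400 mg and 8000 mg include patients enrolled before Amendment 6 and 1200 mg does not.

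The clinical consequences of immunogenicity are an important potential risk in Protocol 3.3.2, and immunogenicity is a secondary objective. The dose rationale in Protocol 3.2.2.1 predicts that at 1200 mg per antibody at least 95% of patients stay above 20 µg/mL for 28 days. The day 29 sample is therefore taken with drug expected to be present, so the day 120 sample could add information. The planned table would largely hide it.

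The sub-classes depend on the schedule too. A positive patient sampled only at day 29 is indeterminate by construction. Scheduled cohort 1 samples at days 29 and 120 are (120 − 29)/7 = 13.0 weeks apart, so none can meet the 16-week rule for persistence.

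**Working it through.** **Inputs from the documents** (Protocol 11.2 and Table 12, patients with at least one risk factor): 662 per arm before Amendment 6 (placebo, 2400 mg, 8000 mg); 1352 per arm under Amendments 6/7 to 24 February 2021 (placebo, 1200 mg, 2400 mg); up to 1500 more from 25 February 2021, 1:1 to the two active doses; about 600 in the PK sub-study.

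**Check of the plan's own figure.** 1352 + 1500/2 = 2102 per active arm, against a stated figure of about 2100. The documents give no ADA rate, so there is none to reproduce.

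**Assumptions.** The sub-study splits 200 per arm; 1% are positive by day 29; a further q = 5 points are first positive at day 120 in every arm (range 1 to 10). Randomized counts stand in for the ADA analysis set, whose size is not given.

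**Formulas.** Late-tested share s = sub-study patients in the arm / all patients in the arm. Pooled rate = 1% + s × q. With everyone tested late, it would be 1% + q.

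| Arm | Patients | s | Pooled rate, q = 5 | All tested late |
|---|---|---|---|---|
| 1200 mg | 1352 + 750 = 2102 | 200/2102 = 9.5% | 1.48% | 6% |
| 2400 mg | 662 + 1352 + 750 = 2764 | 200/2764 = 7.2% | 1.36% | 6% |
| Placebo | 662 + 1352 = 2014 | 200/2014 = 9.9% | 1.50% | 6% |
| 8000 mg | 662 | 0% | 1.00% | 6% |

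**Dilution.** The shortfall is q × (1 − s). For q = 1 to 10 it is 0.90 to 9.05 points (1200 mg), 0.93 to 9.28 (2400 mg) and 1 to 10 (8000 mg). At q = 0 it is zero.

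**Artefact between arms with equal true rates.** This is q × (s₁ − s₂).

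- 1200 minus 2400 mg: 0.11 points at q = 5, against a sampling standard error of about 0.34. For q = 1 to 10 it is 0.02 to 0.23 points.
- If all 600 entered after 25 February (300 per active arm), the shares are 14.3% and 10.9%, with placebo at 0%. The gap is then 0.03 to 0.34 points.
- If the rest of the planned 8500 are also added to the arms used before Amendment 6, (8500 − 1986 − 4056 − 1500)/3 ≈ 319 per arm, the gap reaches 0.45 points at q = 10.
- 1200 minus 8000 mg: 0.48 points at q = 5 (standard error about 0.50). For q = 1 to 10 it is 0.10 to 0.95 points with 200 per arm, and up to 1.43 if all 600 entered late.

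Among concurrently randomized arms the share is equal in expectation (200/2102 in both active arms on the equal split), so the artefact is zero there.

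**The case against.** The best defence is that this output is descriptive, with no ADA test between doses, and that the any-post-dose rule is stated openly. The day 29 rate is correct as a day 29 rate. Time point is a listed immunogenicity variable in both documents, and titers are to be listed for every patient with a pre-existing, treatment-emergent or boosted response. The corresponding bullet in Protocol 11.4.8, "percent (%) of treatment-emergent ADA positive patients by treatment groups and ADA titer categories", breaks off mid-phrase in the text available, so it is weak evidence that no time split was meant. All of this stands, but the SAP bullet is complete and has no split, and a listing does not supply the number tested at each visit.

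A reader might infer three stronger things that the documents do not support.

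- **That the reported rates are too low as a matter of fact.** This needs ADA first detectable after day 29. The documents give no late-onset rate and no drug tolerance for the assay; drug being present at day 29 does not show that the assay misses ADA.
- **That the table would create a false ordering between 1200 and 2400 mg.** Once the planned 750 per active arm are counted, the gap is about a third of a standard error in the example, and placebo comes out highest. The larger contrast is with 8000 mg, which was never randomized concurrently with 1200 mg and is not in the testing hierarchy.
- **That the SAP itself pools day 90 samples.** It does not. Those draws appear only in the Amendment 10 US protocol, testing of pediatric samples is subject to feasibility (Protocol 9.2.9), and no count of affected 12- to 17-year-olds is given.

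Two further limits. Protocol 6.1.3.1 says that patients enrolled before Amendment 6 re-consent to Table 5, but this does not place them in the PK sub-study. At the 18 February 2021 data cut, few day 120 results could exist: the phase 2 lock that preceded Amendment 6 was on 24 October 2020, 117 days earlier. The mixing matters for later analyses.

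**Conclusion.** The mixed denominator is real and follows from the SAP's own rules. Its main effect is dilution, conditional on some ADA first appearing after day 29: roughly nine in ten or more of each arm could not show it. With 200 sub-study patients per arm, 1% by day 29 and 5 later points, the table would show about 1.5% (1200 mg), 1.4% (2400 mg), 1.5% (placebo) and 1.0% (8000 mg) instead of 6%. The split, the day 29 rate and the late rate are all assumed. Distortion between the two main doses is small, and any misleading order is mainly against 8000 mg. This is an inexpensive improvement in reporting; it does not affect the efficacy conclusions.

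**What to change.** In SAP 5.10.1 and 5.10.2, and in Protocol 11.4.8:

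- Report ADA and NAb by nominal visit, with the number tested at that visit as the denominator.
- Use day 29 in all patients as the between-arm summary.
- Report the cumulative rate through day 120 only in concurrently randomized PK sub-study patients who have a day 120 result, and show that number per arm.
- Keep late samples from cohort 2 and cohort 3 separate, by cohort and by day 90 or day 120. Do not pool the two days, and divide by patients tested, not patients scheduled.

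The cost is SAP wording and an added table, with no new data. The downside is precision: on an equal split, a 6% rate in 200 patients has a standard error of √(0.06 × 0.94/200) = 1.7 points, or about ±3.3 points at 95%.

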In addition to these procedures, previously described assessments (separate from the long COVID portion of the study) will be performed at day 120 and day 169 safety assessments, and (for those who were enrolled in the PK sub-study) an additional blood draw will be collected at day 120 for analysis of drug concentration and immunogenicity. These assessments are separate from the long COVID portion of the study.

Additional information concerning the procedures to be performed is provided in Section 9.2.16. Rationale for the study is provided in Section 3.2.1.6.

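### In adults the 'persistent' ADA category cannot be reached: it needs positives 16 weeks apart, but the scheduled post-dose ADA samples are at most 13 weeks apart

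*SAP*

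**What the plan says.** SAP 5.10.1 defines three sub-categories of treatment-emergent ADA response and commits to reporting the number and percentage of subjects in each.

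- *Persistent*: "two or more consecutive ADA positive sampling time points, separated by at least 16week period (based on nominal sampling time"), with no negative sample in between.
- *Indeterminate*: "Treatment-emergent ADA positive response with only the last collected sample positive in the ADA assay".
- *Transient*, the residual: "Treatment-emergent ADA positive response that is not considered persistent or indeterminate, regardless of any missing samples".

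All three sit under the parent definition, which the SAP shares with Protocol 11.4.8: "Treatment-emergent response, defined as an ADA positive response in the ADA assay post first dose when baseline results are negative or missing". The three-way split itself appears only in the SAP.

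For adults, the ADA sampling days come from Protocol Tables 5 to 7 and SAP 10.1. Cohort 1 patients outside the PK sub-study have a pre-dose and a day 29 sample. For the sub-study, Protocol 6.1.3.2 states that "an additional blood draw will be collected at day 120 for analysis of drug concentration and immunogenicity", and Protocol 9.2.8 says of the roughly 600 sub-study patients: "Additional samples for immunogenicity assessment will be also collected in these patients". Cohort 3 adults are sampled pre-dose and on days 29 and 120 (Protocol Table 7). No adult schedule has an ADA sample on day 169.

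**The concern.** A persistence criterion is useful only if the sampling schedule can satisfy it. Here the required separation is longer than the longest interval between two scheduled post-dose ADA samples in any adult. The persistent row is then zero by construction, and because transient is the residual, it absorbs patients who were still positive at their last ADA sample.

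Immunogenicity is a stated secondary objective for cohorts 1 and 3 (Protocol 2.2, SAP 1.2.2). A report showing 0% persistent and some percentage transient would read as a finding that antibodies, where they arose, went away. The design cannot support that statement, and the label would hide evidence to the contrary.

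The point concerns adults only (cohort 1, and cohort 3 aged 18 or over). Nothing is claimed about cohort 2.

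**Working it through.** The 16 weeks is a definition, not a derived figure, so there is nothing to reproduce beyond the conversion 16 × 7 = 112 days.

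**Inputs**

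- Required separation: 112 days on nominal time (SAP 5.10.1).
- Baseline negative or missing (SAP 5.10.1, Protocol 11.4.8). A positive pre-dose sample cannot be one of the pair, so the pre-dose to day 120 span does not count.
- Post-dose ADA days: 29 only (cohort 1 outside the PK sub-study); 29 and 120 (sub-study and cohort 3 adults).
- Windows: ±3 days at day 29 (Protocol Tables 5 and 7). Protocol 9.1.1, footnote 12: "For samples collected on day 120, the collection window is" ±28 days.

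**Step 1: longest nominal gap**

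- Sub-study and cohort 3 adults: 120 − 29 = 91 days; 91 / 7 = 13.0 weeks. Shortfall: 112 − 91 = 21 days.
- Other cohort 1 adults: one post-dose sample, so no gap exists.

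**Step 2: what a qualifying pair would need**

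- A second sample on nominal day 29 + 112 = 141 or later, or
- a first post-dose sample on nominal day 120 − 112 = 8 or earlier.

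Neither is scheduled for adults.

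**Step 3: labels for every positive pattern**

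| Day 29 | Day 120 | Label under SAP 5.10.1 |
|---|---|---|
| + | + | transient (91 < 112, and not only the last sample is positive) |
| + | − | transient |
| − | + | indeterminate |
| + | no sample | indeterminate |

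The first two rows are clinically opposite and get the same label. Outside the sub-study, a treatment-emergent positive in cohort 1 can only be indeterminate.

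**Step 4: do visit windows help?**

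- Shortest actual gap: (120 − 28) − (29 + 3) = 92 − 32 = 60 days = 8.6 weeks.
- Longest actual gap: (120 + 28) − (29 − 3) = 148 − 26 = 122 days = 17.4 weeks.

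Some patients could exceed 16 weeks in real time, but the rule uses nominal time, so they still cannot qualify.

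**Step 5: other routes to a sample**

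- Withdrawal after day 29 triggers end-of-study collections (Protocol 9.1.2), which include no adult ADA sample.
- Unscheduled blood may be drawn (Protocol 9.1.3), but it has no nominal day, and SAP 6.4 applies no visit windows to immunogenicity data.

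**Step 6: reading of the tables**

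Some table marks are displaced in the available text. The SAP 10.1 row for pregnant adults appears to carry two ADA marks where Protocol Table 7 carries three. The conclusion does not depend on this: fewer marks make the category no more reachable, and an extra mark between days 29 and 120 could not widen the 91-day span.

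**Step 7: size**

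The documents give no ADA incidence. As an assumption only, if 1% to 5% of the 600 sub-study patients were positive at both visits, 600 × 0.01 = 6 to 600 × 0.05 = 30 patients would be tabled as transient while still positive at their last ADA sample. This counts all arms together and assumes that every patient has both samples.

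**The case against.** The strongest reply is about weight. The split is descriptive and is absent from Protocol 11.4.8. Persistence is not among the immunogenicity variables in SAP 4.9 and is not named in the association analyses of SAP 5.11. No ADA endpoint is in the testing hierarchy. SAP 5.10.1 also promises: "Listing of all ADA titer levels will be provided for subjects with pre-existing, treatment-emergent and treatment-boosted ADA response". A reader could therefore recover the +/+ pattern from the listing. All of this stands and limits the consequence. It does not make the tabulated rows correct.

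The 6 to 30 illustration is also open to criticism. The incidence is assumed, some of the 600 received placebo (allocation was 1:1:1 until 25 February 2021), tables are by arm, and not everyone will have both samples. That is fair. The figure shows scale only, and for a given incidence it leans high.

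A third point is timing. The SAP's primary data cut is 18 February 2021. Day 120 falls 119 days after day 1, so reaching it by then requires dosing by 22 October 2020. The sub-study arrived with amendment 6, which was written after the phase 2 analyses (database lock 24 October 2020). If ADA used that cut, no sub-study patient would have reached nominal day 120, and only early-window samples could exist. The mislabelling would then bite in later reporting. The documents do not state the ADA cut, so this may delay the problem but does not remove it.

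Finally, lowering the threshold to 13 weeks because the schedule allows it has no documented scientific basis. That is a good reason to prefer an unlabelled pattern table, but not a reason to keep a criterion that nobody can meet.

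**Conclusion.** The concern holds. Followed as written, SAP 5.10.1 will report 0% persistent ADA in adults regardless of the data, because the longest nominal gap is 91 days against the required 112. It will also label as transient any adult positive on both day 29 and day 120. The conclusion rests on the nominal-time wording, the negative-or-missing baseline condition, and the absence of an adult ADA sample by post-dose nominal day 8 or from nominal day 141 onward.

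The mix-up of sustained and lost responses is confined to patients with a day 120 sample: about 600 in the PK sub-study, plus cohort 3 adults, for whom there is no enrolment target. How many will be mislabelled cannot be derived from the documents. Efficacy, type I error, treatment-emergent totals and titre summaries are unaffected. It should be corrected before the ADA tables are produced, because the printed rows would otherwise mislead.

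**What to change.** In SAP 5.10.1, for adults, do one of the following:

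- Preferred: tabulate the day 29/day 120 pattern (+/+, +/−, −/+) without persistent or transient labels. This avoids choosing a new threshold.
- Alternatively, replace the 16-week criterion with positive at both nominal day 29 and nominal day 120, and label it as 13 weeks nominal.

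In either case, restrict the breakdown to patients with a day 120 sample, report only treatment-emergent yes/no for the rest, and list actual sampling days. Add a table footnote saying that the adult schedule cannot support a 16-week definition.

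The cost is one or two sentences and the footnote. No new samples are needed, and Protocol 11.4.8 needs no change because it does not contain the split. The drawback is that results will no longer match the 16-week definition, and actual gaps will still vary with the ±28-day window.
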